Aim 1: Evaluate comparative effectiveness of two patient decision aids (a long PDA versus a short PDA) and a surgeon-focused intervention (usual care versus intervention, a summary that includes patients' goals and treatment preferences) on their ability to achieve high decision quality.

Hypothesis 1.1: Overall, patients who receive the long PDA will have higher decision quality than those who receive the short PDA.

Hypothesis 1.2: Patients who receive the long PDA, with more comprehensive information and videos to make the information more salient, will have higher knowledge scores than those who receive the short PDA.

Hypothesis 1.3: More patients who receive the short PDA, with the explicit values clarification exercise, will have a clear treatment preference than those who receive the long PDA.

Aim 2: Follow participants for 12 months to determine the impact of the decision support strategies on treatment choices and health outcomes, specifically, overall quality of life and functional status.

Hypothesis 2.1: Patients with high decision quality (i.e. informed and received preferred treatments) at one week will have better health outcomes at one year compared to those with low decision quality.

Hypothesis 2.2: Patients with high decision quality at one week will have lower surgical rates at one year compared to those with low decision quality.

Aim 3: Identify patient-, physician- and intervention-level factors associated with effectiveness for the PDAs. These factors include (1) patient characteristics (e.g. age, gender, education level, and joint (hip or knee)), (2) provider characteristics (e.g. years since graduation, surgical volume), (3) intervention compliance (e.g. whether patients reviewed the decision aids and amount of time spent reviewing the decision aids) and (4) mode of delivery (online or hardcopy).

BACKGROUND AND SIGNIFICANCE

Provide a brief paragraph summarizing prior experience important for understanding the proposed study and procedures.

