14. About 6 months from the date of their initial visit, study staff will confirm participant surgical status and will send participants the third survey (T3) by mail or email. Non-surgical patients will receive T3 about 6 months from their consultation and surgical patients will receive T3 about 6 months from their surgery date. Study staff will follow up with a phone reminder within 1 week, a second mailing or up to three reminder emails as appropriate, and a second phone reminder for non-responders. For those who do not respond to the email reminders, we will mail them a survey before the second phone reminder.

15. All patients who receive the final survey will also be able to indicate their consent to be contacted in the future for other studies run out of the Health Decision Sciences Center. Of those patients who've given consent to be re-contacted: study staff may contact these patients via email or telephone, depending on their preferred method indicated, to invite them to participate in future projects and studies.

16. Study staff will review completed surveys soon after receipt and enter survey data into the study database as needed. If there are large portions of the surveys that are missing the study coordinator will contact the participant to determine whether the items were intentionally skipped

(in which case no further action will be taken) or whether it was not intentional and in this case will provide any needed clarification and request that the items be completed.

17. All participants who complete the T3 survey will receive a thank you note including an answer key to the knowledge section of the T1 and T2 surveys.

18. Study staff will collect additional data from the medical record (including patient demographics, treatments received for the hip/knee, co-morbidities, and clinician visits related to the hip/knee) in the 12 months since the initial visit, patient-reported quality of life and functional status data from the Harris Joint Registry and Newton Wellesley Hospital's Kaplan Joint Center registry (IRB# 2014P000696) databases, and use of decision aids from the Shared Decision Making database (IRB 2005p-002282).

19. Limited data will be kept on non-responders including joint, age, gender, physician, decision aid assignment, reason for refusal (if available), and all elements in the eligibility screener. This information will be used to examine non-response bias.

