20. Study data will be cleaned, surveys will be scored, analyzed and manuscripts will be prepared for publication.

Clinician surveys:

Participating clinicians will complete a short survey for a subset of their participating patients. The survey will include questions about satisfaction with the visit and rating of the quality of the decision. Research coordinators will approach the clinician in person with paper survey shortly after the initial visit. If they are not able to connect in person, they will send an email with the survey for each patient and will make up to three reminders via email to encourage the surgeon complete the survey.

All study staff are CITI certified and will receive training from the PI and program manager in the study protocol.

Outcomes:

This study will capture three main types of outcomes – these include patient-reported measures related to decision making (e.g. decision quality, decision making process and regret), patient-reported health outcomes (e.g. knee and hip pain, quality of life and functioning) and medical treatments received by participants.

We will collect the measures listed below. Table 3 shows the measures assessed at each time point as part of this study and the estimated burden on participants.

Measures:

Decision Making Measures (timing of use)

1. Hip OA and Knee OA Decision Quality Instruments (T1, T2, T3): Each DQI contains 5 decision-specific, multiple-choice knowledge items, 5 decision-specific goals and concerns (rated on an 11 point importance scale), one treatment preference item. The DQI results in a knowledge score (0-100%) and a concordance score (0-100%) indicating the percentage of patients who received treatments that matched their stated preference, and an involvement score (0-100%) with higher scores indicating more patient involvement in decision making. The minimal important changes (MIC) in knowledge and concordance scores are 10% (14).

2. Decision Process Score (T2, T3): 7 items that assess the decision-making process including whether options, outcomes and preferences were discussed. A total score is generated and scaled to (0-100%) with higher scores indicating more patient involvement in decision making. 3 items that assess general satisfaction with the visit.(9)

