- 9. PDA use (T1, T2):** items will assess how much of the DVD, booklet and/or website was reviewed (all, some, a little, none) and how much time did they spend reviewing it (0-5 minutes; 6-10 minutes; 11-20 minutes; 21-30 minutes; >30 minutes).
- 10. Treatment received (T3, chart review):** surgical and non surgical treatments tried in the twelve months after the visit will be self reported by patients and also collected via chart review.
- 11. Expectations (T2, T3):** 4 items will assess expectations for pain relief, limitations in daily activities, overall success of surgery and complications (29).
- 12. Demographics (T2):** information such as education, employment, marital status will be self reported.
- 13. Satisfaction (T2, T3):** questions to assess overall satisfaction with quality of visit or treatment outcome
- 14. Information use (T3):** 1 question to assess what sources of information patient about their health condition they found important
- 15. IMPACT index (T2, T3):** 7 items assessing the impact of hip and knee osteoarthritis on patients' perception of their condition: worry, pain, limitation, confidence, and involvement in decision making.

Table 3: Measures including in surveys

Measures	Pre-visit (T1)	~ 1 week (T2)	~ Follow-up (T3)
Visit goals and functional goals	2 (physician intervention group only)		
		12	

Decision Quality Instrument	9		0
Decision aid use	1	1	Not asked
Decision making process	0	11	7
Functional goals	Not asked	2	1
SURE	Not asked	4	Not asked
Expectations	Not asked	10	10
Quality of life, pain and functioning (KOOS or HHS, EQ-5D)*	Routinely collected	Not asked	Routinely collected
Decision Regret	Not asked	Not asked	5
Satisfaction	Not asked	1	2
Demographics and treatment history		5	2
Health literacy	1	Not asked	Not asked
Impact Index	Not asked	7	7
Total number of items	13 (MD usual care group)/ 15 (MD intervention group)	53	34
Total time estimate	5 minutes	15 minutes	15 minutes

*These items are asked as part of routine care at this time point.

Randomization and blinding

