For patient-reported outcomes (decision quality, quality of life, etc.), missing data items will be handled per established protocols for the validated surveys (e.g., missing knowledge items are considered incorrect). For item-specific analysis, our primary analyses will be conducted excluding patients with missing data. The treatment received (surgical vs non-surgical) will be assessed through chart review and confirmed via patient report (T3); therefore, is not subject to missing data. Even though we cannot test the missing at random assumption, we will first compare patients with and without missing data to gain insights. As a sensitivity analysis, we will conduct several missing imputation techniques: (1) last value carried forward (LVCF), (2) single imputation with EM algorithm and (3) multiple imputation. The LVCF approach applies to follow-up missing data, which is essentially the same as assuming no change over time. Compared with single imputation, the appealing aspect of the multiple imputation approach is incorporating the variability across imputation so that the statistical uncertainty due to missing is more properly accounted for. We will compare our findings from the primary analyses with the findings from different imputation strategies to determine whether our findings are stable across different assumptions. We will also report the uncertainty associated with the treatment effect as indicated in the SE estimates from the multiple imputation analysis.

As the first step, responders and non-responders will be compared across groups to examine non-response bias. For patient-reported outcomes, missing data will be handled per established protocols for the validated surveys. We will conduct sensitivity analyses to determine the impact of missing imputation.[3] The hypotheses will be evaluated using an intention-to-treat approach. The analysis plan for the primary outcome (hypothesis 1.1) will first calculate the rate of decision quality in each group, as the percentage of patients who meet or exceed the knowledge

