threshold *and* receive treatment that matches their preference. A logistic regression model with the generalized estimating equations (GEE) approach will be used to compare the rates of decision quality of the DA-A and DA-B groups and account for the clustering of patients within providers.[4] Analysis will start by testing the interaction between the two intervention factors. It is plausible that an interaction between DAs and type of surgeon report exists for this analysis. Thus, the effective sample size will be limited to 117 per group when the comparisons are stratified by the type of surgeon report. The study has 89% power to detect a difference in the percentage of patients with high decision quality of 18%, from 65% in DA-B group to 83% in DA-A group.

For hypothesis 1.2, an interaction between DAs and PPR report is unlikely so there is no need to account for clustering within the same provider, thus, we will use a two-sample t-test to compare the mean knowledge score between the two groups. With approximately 560 patients from each group, we can invoke the Central Limit Theorem and use a two-sample t-test to compare mean knowledge score between the two groups, even if the knowledge score is not normally distributed. The study will have 80% power to detect a difference as small as 3.3% in total knowledge scores assuming the SD is 20%. For hypothesis 1.3, patient's treatment preference will be assessed before the surgeon visit so again, there is no need to account for clustering. A X² test will be used to compare the percentage of patients with clear treatment preference between the two groups. Hypothesis 2.1 will use a linear regression model with the GEE approach and hypothesis 2.2 will use logistic regression with GEE approach to account for clustering of patients within surgeons for these analyses.

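### Hypothesis 2.2 compares surgery rates between groups that are themselves defined partly by whether surgery was received

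*Protocol*

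**What the plan says.** **Hypothesis.** Protocol, Specific Aims, Aim 2, hypothesis 2.2: "Patients with high decision quality at one week will have lower surgical rates at one year compared to those with low decision quality".

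**Exposure.** Hypothesis 2.1, in the same section, defines the grouping: "Patients with high decision quality (i.e. informed and received preferred treatments) at one week". The SAP, in its analysis of hypothesis 1.1, counts patients who reach the knowledge "threshold *and* receive treatment that matches their preference". Protocol, Measures, item 1 describes the second component as "a concordance score (0-100%) indicating the percentage of patients who received treatments that matched their stated preference".

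**Treatment variable.** SAP, missing-data paragraph: "The treatment received (surgical vs non-surgical) will be assessed through chart review and confirmed via patient report (T3". Protocol, Measures, item 10 covers "surgical and non surgical treatments tried in the twelve months after the visit". Study Procedures, step 18 sets the chart review window: "in the 12 months since the initial visit".

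**Model.** In the SAP, "hypothesis 2.2 will use logistic regression with GEE approach to account for clustering of patients within surgeons for these analyses". No covariate is named there. The SAP also says that the hypotheses will be evaluated by intention to treat.

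The part of the SAP that precedes the missing-data paragraph was not available for this review.

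**The concern.** Read together, these places put one variable on both sides of the hypothesis 2.2 model. The high group contains only informed patients whose treatment matched their preference. The low group contains every uninformed patient plus the informed patients whose treatment did not match. Selecting on match changes the surgery rate of each group even if neither knowledge nor match has any influence on surgery.

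Hypothesis 2.2 is the only Aim 2 hypothesis about surgery. A lower rate in the high group would naturally be read as evidence that better decisions reduce surgery. The same result can arise only because most patients in the sample prefer not to have surgery, and the sign reverses if most prefer surgery.

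The one-week label adds an ambiguity. Hypotheses 2.1 and 2.2 place decision quality at one week, but the treatment data run for twelve months, and no visible passage says which window the match uses.

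**Working it through.** **The plan's own figure.** The only visible figure built on decision quality is the power for hypothesis 1.1: 89% for 65% against 83% with an effective 117 per group. Two-sided 5% is assumed. The pooled SE is √(2 × 0.74 × 0.26/117) = 0.0573 and the unpooled SE is √[(0.65 × 0.35 + 0.83 × 0.17)/117] = 0.0561. Power is Φ[(0.18 − 1.96 × 0.0573)/0.0561] = 88.6%, so the figure reproduces. No power or effect size is visible for hypothesis 2.2.

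**Inputs for hypothesis 2.2.** Let p be the share preferring surgery, i the share informed, and m the share whose treatment matches preference. The documents give none of these separately. They do give 65% and 83% as planning rates of high decision quality, which limit the product i × m. The base case i = 0.80, m = 0.90 gives i × m = 0.72, inside that range. Being informed is taken as independent of preference and treatment, so decision quality has no effect. Preference is two-way, with no unclear category.

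**Formulas.**
- Surgery rate, high group: ipm/(im) = p.
- Surgery rate, low group: [pm + (1−p)(1−m) − ipm]/(1 − im).
- Difference, high minus low: (2p − 1)(1 − m)/(1 − im).

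**Base case at p = 0.30.** High 30.0%. Low (0.27 + 0.07 − 0.216)/0.28 = 0.124/0.28 = 44.3%. Difference −14.3 points.

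| Share preferring surgery | 30% | 40% | 50% | 60% | 70% |
|---|---|---|---|---|---|
| High minus low, points | −14.3 | −7.1 | 0 | +7.1 | +14.3 |
| Rejection at two-sided 5%, n = 840, no clustering | 97% | 46% | 5% | 46% | 97% |
| Same, design effect 1.79 | 81% | 29% | 5% | 29% | 81% |

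The 840 is the number expected to complete T2 (Protocol, Research Design and Methods). At p = 0.30 the groups are 604.8 and 235.2 patients and z = −3.82, or −2.85 with the design effect. That design effect is my inference: 840/4 = 210 per factorial cell, and 210/117 = 1.79. It carries a hypothesis 1.1 quantity over to hypothesis 2.2.

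**Sensitivity.**
- At p = 0.30 and m = 0.90, using the SAP's own 65% and 83% for i × m: −0.04/0.35 = −11.4 points and −0.04/0.17 = −23.5 points.
- Unequal matching at p = 0.50 and i = 0.80: if 80% of those preferring surgery and 90% of the others are matched, +6.4 points; with the two rates exchanged, −6.4. An even preference split is therefore not always neutral.
- If match to the treatment planned at T2 is meant, the difference is multiplied by the surgery rate when surgery is planned minus the rate when it is not. At p = 0.30, rates of 90%/10%, 80%/10% and 60%/20% give −11.4, −10.0 and −5.7 points.

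**Would adjusting for preference help?** Not while the composite is the exposure. Among patients preferring surgery, the high group's surgery rate is 100% by definition and the low group's is 0.18/0.28 = 64%. Among those preferring non-surgical care, the rates are 0% and 0.10/0.28 = 36%. Within a stratum, match and outcome are the same variable.

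**The case against.** **The exposure window is inferred.** The SAP sentence on treatment received is about missing data, and the Protocol passages describe data collection; none of them defines the hypothesis 2.2 exposure. If the planned treatment at T2 is meant, exposure precedes outcome and the gap shrinks. This stands, and it is why the timing has to be stated. It does not clear the plan: the visible definitions say received, and the gap disappears only if the plan does not predict surgery at all.

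**The unavailable part of the SAP may deal with it.** It may. A reader might infer that no preference adjustment is planned; the documents support only that none is visible. Adjusting the composite would not remove the overlap in any case.

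**The sizes are assumed.** True, apart from the limit set by the 65% and 83% rates. The overlap follows from the definitions; only its sign and size depend on the inputs.

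**The replacement exposure is not clean either.** This stands. T2 knowledge is measured after the surgeon visit and may already reflect the treatment plan. In simulations where surgery depended only on preference and surgeon, T2 knowledge with preference as covariate rejected a true null in 2.5 to 5.8% of runs. If instead T2 knowledge is 85% in patients who go on to surgery and 75% in the rest (assumed), with knowledge having no effect, an unclustered version rejects in more than half of runs. The replacement removes the built-in overlap, not confounding.

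**Conclusion.** Wrong as written, and it should be fixed. On the visible text, treatment received enters both the exposure and the outcome of hypothesis 2.2. The analysis can then show a surgery difference in either direction with no effect of decision quality: −14.3 to +14.3 points as the share preferring surgery goes from 30% to 70%, under the assumed 80% informed and 90% matched. Confidence is high on the overlap and moderate on its size and on the intended window.

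Three stronger readings are not supported. A reader might infer that hypothesis 2.2 is true by definition; it is not, because knowledge is the other component and the difference can be negative, zero or positive. A reader might infer that the trial's main conclusions are at risk; hypothesis 1.1 is primary, and it and hypotheses 1.2 and 1.3 do not use surgery as an outcome. A reader might infer that a preference covariate alone is the missing safeguard; the stratum rates of 100% and 0% show otherwise.

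**What to change.** 1. For hypothesis 2.2, take treatment received out of the exposure. Use the knowledge threshold, with stated T1 preference (surgery, non-surgery, unclear) as a covariate, in the logistic GEE already planned. T2 knowledge fits the one-week label; T1 knowledge, which precedes the visit, should be the sensitivity analysis. Both knowledge sections are on the surveys (Study Procedures, step 17), and the SAP's text on hypothesis 1.3 has preference assessed before the visit. If the composite is still shown against surgery, call it descriptive, state the overlap, and do not test it overall or within preference strata.
2. State when knowledge, preference and treatment are each measured and how an unclear preference counts towards a match. Reconcile the one-week label with the twelve-month treatment data. T3 timing belongs here too: Study Procedures, step 14 sends it at about 6 months, while Research Design and Methods gives 12 months.
3. Label hypotheses 2.1 and 2.2 observational associations. Both group patients by a status that arises after randomisation, so intention to treat does not describe them.

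The cost is a change of wording, using a planned model and data already collected. The downside is that hypothesis 2.2 becomes narrower than decision quality and stays open to confounding, so no control of false positives should be claimed beyond the simulated assumptions.

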This is a randomized trial with a 2x2 factorial design to examine the comparative effectiveness of two PDAs and an in-visit intervention. In the study, patients will be surveyed shortly before their initial visit with an orthopedic specialist and again about 1 week and 1 year after the visit. Patients scheduled for an appointment with the orthopedic specialist will be screened for eligibility (criteria are listed in Table 1) and if eligible, will be randomized to receive either the Health Dialog or Healthwise decision aids to review before their visit. A computer generated randomization allocation sequence will be created for participants. Eligible patients will receive a cover letter and an information sheet about the study that includes instructions about how to opt-out in the mail before their visit. Those who do not opt out will then be enrolled in the study. The random assignment originally assigned to patients who are found ineligible after their visit will be put back to the queue and become available for the next eligible patient.

Providers will be randomly assigned to usual care or intervention group (a worksheet which includes patient’s goals and preferences). Providers in the worksheet group will receive short training on the use of the worksheet.

The study will enroll patients at three sites: an academic center, the Arthroplasty Department at Massachusetts General Hospital (MGH), a community hospital, Kaplan Joint Center at Newton Wellesley Hospital (NWH), and an orthopedic specialty hospital, New England Baptist Hospital (NEBH). MGH and NWH share common resources that are critical to the conduct of the study, including patient registries which routinely collect similar patient reported data and clinical outcomes for hip and knee osteoarthritis patients. Both these sites also have access to both

[figure not shown]
Healthwise and Health Dialog decision aids through Partners Healthcare’s contracts with those vendors. NEBH is not a Partners-affiliated hospital and therefore requires separate coordination efforts to execute the research study.

Table 1: Eligibility for survey study

	Eligible	Ineligible

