5. The staff at Health Decision Sciences Center will send the assigned decision aid, cover letter, information sheet, and appropriate survey (depending on provider assignment) to eligible patients in advance of their upcoming visit in the arthroplasty service. The letter will include information about how to opt-out of the study. The packet for subjects will include the survey (T1) so they have the option of completing the survey at home and bringing it with them to the visit.

6. Two days before the scheduled visit, study staff may call subjects who did not opt out to answer any questions about the study, and to remind them to review the decision aid before the visit, and complete the survey. Study staff can administer the survey over the phone if the patient prefers to do so.

7. On the day of the visit, the study staff will discuss the study with the eligible patients who did not opt-out. If the patient agrees to participate, then study staff will administer the survey either on paper or electronically if tablet or computer is available.

8. By completing this first assessment, participants will give consent to enroll in the study.

9. Study staff will work with the Harris Joint Registry at MGH and NWH data registry to download the completed quality of life and the study questionnaires for all participants.

10. The surgeon will receive the enhanced report (depending on their study assignment) for their participating patients.

11. A research coordinator will review medical record after the visit to complete the eligibility screener, as needed, and will send the second survey (T2) by mail or email within a week of the specialist visit to all confirmed eligible patients who did not opt out. If patients have not completed the routinely collected quality of life while at their visit, it will be included with this survey.

12. Study staff will follow-up with a phone reminder about one week after sending the survey, followed by a mailed reminder or up to three email reminders, and a second phone reminder for all the participants who did not complete the surveys. Participants who are receiving the survey by email will also get one mailed reminder if it is not completed in two weeks. Patients will be given the option to complete the survey by phone.

13. All participants who complete the T2 survey will receive a thank you note.

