Provider randomization will be stratified by site. Within each site, surgeons will be divided into two groups with similar patient volume. One of the two groups will be randomly assigned to usual care and the other to receive the in-visit worksheet. It will not be possible to blind the research staff, patient or providers to the group assignment for providers; however, those entering data and those analyzing the data will be blinded to group assignment.

A computer-generated randomization allocation sequence will be created for patients from each site. After confirming eligibility, the staff at the Health Decision Sciences Center that fulfills PDA orders will have access to the sequence in order to deliver the appropriate decision aid. The staff who fulfill the orders will not be the same staff that approach patients in clinic. To the extent possible, the research staff calling participants on the phone and/or approaching them in clinic will be blinded to the PDA assignment. In our pilot, several patients brought the decision aid to the clinic with them, and as a result, it was clear which intervention they received. Patient participants have the opportunity to opt-out before their visit, and those who do not opt out will be enrolled in the study. The random assignment originally assigned to subjects who are found ineligible will be put back to the queue and become available for the next eligible subject.

Patient participants will not be blinded to the PDA assigned to them; however, they will not be given any explicit information on the surgeon assignment. Likewise, surgeons will not be blinded

to their intervention group, but they will not be given any information on the type of PDA the patient used. The study staff doing chart review and data entry will be blinded to the patient and provider assignments to avoid unintended bias. The statistician analyzing the data will also be blinded to the study assignments.

For studies involving treatment or diagnosis, provide information about standard of care at Partners (e.g., BWH, MGH) and indicate how the study procedures differ from standard care. Provide information on available alternative treatments, procedures, or methods of diagnosis.

This study involves reviewing patient educational materials, completing surveys and conducting medical chart review. No diagnostic tests or treatments will be offered or administered as part of this study.

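### Reissuing the assignment of a patient found ineligible after the visit can reveal the next patient's arm and hides exclusions that differ by arm; use each assignment once

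*Protocol*

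**What the plan says.** The rule appears twice in the protocol. Research Design and Methods has: "The random assignment originally assigned to patients who are found ineligible after their visit will be put back to the queue", after which it will "become available for the next eligible patient". Randomization and blinding repeats it without tying it to the visit: "The random assignment originally assigned to subjects who are found ineligible will be put back to the queue".

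Study Procedures gives the order of events. The PDA and first survey are mailed before the visit (step 5), completing that survey is consent and enrollment (step 8), and eligibility may be settled only later (step 11): "A research coordinator will review medical record after the visit to complete the eligibility screener, as needed".

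Randomization and blinding also describes the safeguards:
- Sequence: "A computer-generated randomization allocation sequence will be created for patients from each site".
- Access: "After confirming eligibility, the staff at the Health Decision Sciences Center that fulfills PDA orders will have access to the sequence".
- Separation of roles: "The staff who fulfill the orders will not be the same staff that approach patients in clinic".
- Staff who review charts and enter data are blinded.
- Staff who telephone or meet patients are blinded only as far as is practicable. In the pilot, "several patients brought the decision aid to the clinic with them, and as a result, it was clear which intervention they received".

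The SAP says that the hypotheses will be tested by intention to treat.

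**The concern.** There are two separate problems.

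**Concealment.** A fresh assignment is unknown to recruiting staff until it is issued. A returned one has been used, and its PDA may have been seen in clinic. The coordinator role screens schedules and may call patients about eligibility (steps 3 and 4) before any PDA is mailed, and completes the screener after the visit (step 11). Someone in that role who learned a returned assignment and knew it was next could let that knowledge affect who is confirmed eligible next.

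**Visibility of exclusions.** A patient can be randomized, sent a PDA, enrolled and surveyed, and then dropped. For hypothesis 1.3 the outcome is measured before the visit, so it may already exist at that point. If exclusions were commoner in one arm, unequal arm sizes would be the first warning. Reuse refills the depleted arm and removes that warning.

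What is at stake is the randomized PDA comparison, which carries the primary hypothesis (1.1).

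**Working it through.** **Plan's own figure.** The documents give no number for the reuse rule. The nearest is the power for hypothesis 1.1: 65% versus 83%, 117 effective patients per group, 89%. With two-sided alpha 0.05 (assumed) and the pooled-variance test:
- Null SE = √(2 × 0.74 × 0.26 / 117) = 0.0574.
- Alternative SE = √((0.65 × 0.35 + 0.83 × 0.17) / 117) = 0.0561.
- Power = Φ((0.18 − 1.96 × 0.0574) / 0.0561) = 88.6%, which reproduces the 89%.

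Reuse does not enter this formula, so the stated power is unaffected.

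**Number of reissued slots.** Let r be the share of assignments returned. Figure 2, which may bear on r, is not in the text available to me, so r is assumed. Reissues = 1,120 × r / (1 − r): 59 at 5%, 124 at 10%, 280 at 20%. The 1,120 is the expected number completing the first survey, used here as a stand-in for eligible patients assigned a PDA.

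**Predictability.** Let k be the chance that the person controlling entry knows a returned slot (also assumed). A known slot is guessed correctly with probability 1 and any other with 0.5, so P(correct) = 0.5 + 0.5 × r × k.

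| r | k = 0.1 | k = 0.3 | k = 1 |
|---|---|---|---|
| 2% | 50.1% | 50.3% | 51.0% |
| 5% | 50.2% | 50.7% | 52.5% |
| 10% | 50.5% | 51.5% | 55.0% |
| 20% | 51.0% | 53.0% | 60.0% |

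**Bias if exploited.** Suppose every known slot is filled with a patient whose chance of the outcome is 80% if the slot is one arm and 50% if it is the other. There is no true effect. Expected bias = (80 − 50) × r × k points. A simulation with 1,120 eligible patients, 1:1 allocation in blocks of 4 and 1,500 runs per scenario gave:

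| Scenario | Formula | Simulated bias | Rejection at 5% |
|---|---|---|---|
| r = 10%, no reuse | 0 | 0.1 | 5.1% |
| r = 10%, reuse, k = 0 | 0 | 0.0 | 5.5% (4.4% with simple randomization) |
| r = 5%, k = 0.3 | 0.45 | 0.5 | 5.5% |
| r = 10%, k = 0.3 | 0.9 | 0.8 | 6.0% |
| r = 10%, k = 1 | 3.0 | 3.0 | 17.8% |
| r = 20%, k = 1 | 6.0 | 5.9 | 56.3% |

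Monte Carlo error near 5% is √(0.05 × 0.95 / 1,500) = 0.6 points (one SE), so the first three rows are compatible with 5%. Patients are treated as independent with complete outcomes. With the smaller effective sample in the SAP, the same bias would move the rejection rate less.

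**Masking.** Assume 15% are excluded in one arm and 5% in the other.
- Without reuse, the first arm's retained share is 0.85 / (0.85 + 0.95) = 47.2%, a visible 47:53 split.
- With reuse, the retained arms return to 50:50. The first arm instead takes (1/0.85) / (1/0.85 + 1/0.95) = 52.8% of all assignments issued (simulated 52.7%), which retained counts do not show.

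Unequal exclusion unrelated to outcome caused no bias with or without reuse (rejection 5.6% and 5.5%). Reuse hides the sign of a possible problem; it does not create the problem.

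**The case against.** The strongest reply is that the leak is narrow. Foreseeing a slot requires knowing the dropped patient's PDA, that the slot was returned, and that it is next. The protocol separates those who hold the sequence from those who meet patients, and it blinds chart reviewers, which arguably covers the step 11 check. Sequence holders can see upcoming assignments with or without reuse. Consent follows receipt of the PDA, so selection at consent does not depend on reuse. Most criteria in Table 1 are facts that a mailed PDA cannot change. All of this stands, and it keeps the likely effect small.

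It does not remove the point. The separation concerns clinic contact; nothing in the available text says whether staff who screen schedules or make eligibility calls learn of a return, or how returns are ordered and logged. The protocol itself reports the unblinding route. Limited data, including PDA assignment, are promised for non-responders, but patients later found ineligible are not mentioned.

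A reader might infer that every reissued assignment is foreseeable with certainty, so that 59 to 280 slots are compromised. The documents do not support that: those are assumed counts of reissued slots, and only those whose assignment was learned are exposed. A reader might also infer that the rule erases exclusions from the record. Nothing says that records are deleted; PDA use and enrollment are held in databases. Only the retained arm counts lose the information.

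**Conclusion.** The point holds in a conditional form. Reuse can make the next assignment known to someone who learned the returned one and knows it is next, and it stops arm counts from revealing exclusions that differ by arm. The available text also leaves open how patients dropped after randomization fit the intention-to-treat statement; part of the SAP could not be read, so that detail may exist there.

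The claim that reuse by itself biases the comparison is not supported. With concealment intact and exclusion unrelated to arm, there was no bias. At 10% returned and 30% known, with every known slot exploited, bias is about 0.8 points. Large effects require every return to be both known and exploited. These sizes rest on assumed values of r and k. The change is worth making because it costs little, not because serious harm has been shown.

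**What to change.** 1. Replace the rule in both protocol sections: each assignment is used once. If the patient is found ineligible, the assignment is retired and the next patient takes the next unused one. Lengthen each site's list to allow for this.
2. Allow exclusion after randomization only on facts that predate mailing (for example diagnosis, prior replacement, prior PDA order), judged by someone blind to PDA. State in the SAP how this fits the intention-to-treat population.
3. Report exclusions after randomization, with reasons, by PDA arm in the CONSORT diagram.
4. Flag any assignment already recycled and repeat hypothesis 1.1 without those patients as a sensitivity analysis.

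The cost is protocol wording, a longer list and a slight random imbalance. For example, take a balanced list of 1,120 / 0.9 ≈ 1,244 assignments (622 per arm) and 10% retired at random (assumed). The difference in retained arm sizes then has an SD of √(2 × 622 × 0.1 × 0.9) ≈ 11 patients, negligible against 1,120.
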